10.1. METHOD OF ASSIGNING SUBJECTS

No specific methods (e.g. randomization, blinding, or stratification) for assigning subjects are used in this clinical investigation plan (CIP). Consecutive subjects at each site meeting all eligibility criteria will be enrolled in this clinical investigation.

10.2. PROCEDURES

Subjects in the clinical investigation will undergo placement of the ReUnion RSA System. Please see the approved IFU and Operative Technique Manuals for a detailed description of the medical device(s) and instrumentation, intended use information and associated risk. Any additional clinically indicated procedures are permitted as deemed necessary by the investigator.

10.3. FOLLOW-UP EVALUATIONS

Subjects in this clinical investigation will be evaluated at Pre-Operative, Operative/Discharge, and at 6 Weeks (4 weeks – 8 weeks), 6 Months (23 weeks – 29 weeks), 12 Months (48 weeks- 56 weeks), 24 Months (100 weeks – 108 weeks) and annually thereafter. The follow-up evaluations will include assessment of device-related AEs/incidents, radiographs and ASES Shoulder Score.

Investigative site personnel will contact subjects prior to their scheduled follow-up evaluations to encourage compliance with clinical investigation visits and participation.

If a subject misses a visit and is outside of the visit window, then every effort should be made to collect data instead of noting the visit as missed.

10.4. SCHEDULE OF EVENTS

Assessment	Pre-Operative	Operative/ Discharge	6 Weeks ^{a, b} (+/- 2 weeks)	6 Months ^{a, b} (+/- 3 weeks)	12 Months ^{a, b} (+/- 4 weeks)	24 Months ^{a, b} (+/- 4 weeks)	Annually ^b
Informed Consent	X						
Demographics & Medical History	X						
Inclusion/Exclusion	X						
Physical Exam	X		X ^c	X ^c	X ^c	X ^c	X ^c
Surgical Procedure		X					
ASES Shoulder Score	X		X ^d	X ^d	X ^d	X ^d	X ^d
Image Evaluation ^{e, f}	X	X	X	X	X	X	X
Subject Disposition ^g			X	X	X	X	X
	Device-Related AEs/Incidents & Reoperations will be collected throughout the course of the clinical investigation.						

	
a. Follow-up visit schedule to reflect Institutions' Standard of Care practicesb. If the subject misses a visit and is outside of the visit window, then every effort should be made to collect data instead of noting visit as missed.c. Evaluation may be collected when subject presents in-clinic for study visit.d. Evaluation can be collected via phone.e. Radiograph collection should follow Institution's Standard of Care practices and no additional x-rays should be made for study purposes.f. CT scans may be collected if part of Institution's Standard of Care practices.g. Subject Disposition assessment will occur at any time point for subject withdrawal prior to the completion of the clinical investigation.
--	-----------------------------------------------------------------------------------------------------------------------------------------------------------------------------------------------------------------------------------------------------------------------------------------------------------------------------------------------------------------------------------------------------------------------------------------------------------------------------------------------------------------------------------------------------------------------------------------------------------------------------------------------------------------------------------------------------------------------------------------------------------------------------------------------------------------------------------------------

Table 1: Schedule of Events

11. Statistical Methods

The 24 months post-operative results for subjects implanted with the ReUnion RSA System will be compared to a historical group and results reported by respective clinical outcome data in the scientific literature. The benchmark sources and values will serve as the control group for the ReUnion RSA System subjects.

Hypotheses are developed to allow for a comparison of 24 months post-operative ASES score results and 24 months effectiveness/performance between these two populations.

The Statistical Analysis Plan (SAP) lists all variables/questions within this clinical investigation. Therefore, no additional “evaluation” chapter is required nor needed for this CIP.

Data will be captured via IBM Clinical Development electronic data capture (EDC) system and statistical analysis will be performed using IBM SPSS. All statistical hypotheses tests will be with confidence levels ($1-\alpha$) of 95% and power ($1-\beta$) of 80%. The significance level (α) is 0.05 and the beta-value (β) is set to 0.20. Therefore, p -values ≤ 0.05 will indicate statistical significance.

Results will be presented using summary tables and optionally supported by graphs. For detailed information per variable, see SAP.

The primary endpoint of the clinical investigation is to demonstrate non-inferiority of the device to the selected literature controls, as measured by the ASES Shoulder Score at 24 Months post-operative. Specifically, the proposed study will test the null hypothesis that the population mean is 71.27 points. The criterion for significance (alpha) is set at 0.05. With the sample size of 10 cases, the clinical investigation will have power of 80.3% to yield a statistically significant result. This computation assumes that the population from which the sample will be drawn has a mean of 71.27 points with a standard deviation of 19.40 points. The observed value will be tested against a theoretical value (lower limit - θ) of 51.87 points. To account for an estimated appropriate overall drop-out rate, Stryker intends to enroll the calculated number of subjects, multiplied by the number of cleared indications (four) to reflect the underlying subject population adequately.

11.1. DETERMINATION OF SAMPLE SIZE

The determination of sample size is based on benchmark sources and values. To account for an estimated appropriate overall drop-out rate, Stryker intends to enroll the calculated number of subjects, multiplied by the number of cleared indications to reflect the underlying subject population adequately. For details, please see Table 2.

Benchmark and Objectives for Clinical Investigation

Endpoint	The non-inferiority (equal or better) of the ASES Score in relationship to the officially cleared indications in comparison to respective clinical outcome data in the scientific literature.			
Estimated drop-out rate	56% (confirmed by Medical Expert, see Cuff et al. [1])			
Benchmark Sources & Values ASES [points]				
Source	No.	n	Mean	Std. Dev.
No.	Title			Comments No.
1	Nolan et al. [2] 2011	71	76.1	NA
2	Naveed et al. [3] 2011	49	65	NA
3	Kelly 2 nd et al. [4] 2012	30	71.8	12.7
4	Patel et al. [5] 2012	28	66.2	21.3
5	Cuff et al. [6] 2012	76	75	NA
6a	Wiater et al. [7] 2014	37	84.9	18.9
6b	Wiater et al. [7] 2014	64	77.1	18.3
7a	Black et al. [8] 2014	33	74	23.8
7b	Black et al. [8] 2014	32	69.7	18
8a	Poon et al. [9] 2014	27	70	NA
8b	Poon et al. [9] 2014	23	68	NA
9	Kiet et al. [10] 2015	53	77	19
10	Steen et al. [11] 2015	24	79.9	20.2
11	Wagner et al. [12] 2015	154	65.0	NA
12a	Crosby et al. [13] 2017	73	55	25
12b	Crosby et al. [13] 2017	29	68	20
13	Vourazeris et al. [14] 2017	86	77.7	NA
14a	Otto et al. [15] 2017	32	58.6	NA
14b	Otto et al. [15] 2017	35	40.8	NA
15a	Mollon et al. [16] 2017	428	84.1	17.1
15b	Mollon et al. [16] 2017	48	78.1	21.8
16	Holschen et al. [17] 2017	44	65.3	20.9
17a	Friedmann et al. [18] 2017	340	86.7	15.8
17b	Friedmann et al. [18] 2017	251	82.1	18.2
18	Williams et al. [19] 2017	17	65.6	NA
Identified Cleared Indications				
No.	Indication			
1	Gross rotator cuff deficiency			
2	Degenerative arthritis			
3	Rheumatoid arthritis			
4	Revision of previously failed shoulder joint replacement			
Explorative Meta-Analysis - ASES (single group)				
Acceptance Criteria				
Confidence Interval (CI)				0.95 (95%) two-sided
Software Used				IBM SPSS V20

Case Processing Summary						
	Cases					
	Valid		Missing		Total	
	N	Percent	N	Percent	N	Percent
Mean ASES ReUnion_RSA_CER	25	100,0%	0	0,0%	25	100,0%
Std.Dev. ASES ReUnion_RSA_CER	15	60,0%	10	40,0%	25	100,0%

Descriptives						
Mean ASES ReUnion_RSA_CER						Statistic
Mean						71,2680
95% Confidence Interval for Mean						Lower Bound Upper Bound
						67,0288 75,5072
Median						71,8000
Std. Deviation						10,26985
Minimum						40,80
Maximum						86,70
Interquartile Range						12,45
Std.Dev. ASES ReUnion_RSA_CER						Statistic
Mean						19,4000
95% Confidence Interval for Mean						Lower Bound Upper Bound
						17,7028 21,0972
Median						19,0000
Variance						9,393
Std. Deviation						3,06478
Minimum						12,70
Maximum						25,00
Interquartile Range						3,30

	
Red line: Pooled mean ASES Blue lines: 95% CI of pooled mean ASES Black line: Pooled median pooled ASES Box: Interquartile Range Green Line: Pooled mean ASES minus pooled std. dev. ASES (19.40) $71.27 - 19.40 = 51.87$ points

--	-------------------------------------------------------------------------------------------------------------------------------------------------------------------------------------------------------------------------------------------------------------------------------------------------------------

[figure not shown]
Acceptance Criteria for Sample Size Calculation	
Significance Level (α)	0.05 (5%)
Power (1- β)	0.80 (80%)
Confidence Interval (CI)	0.95 (95%)
Tails	2
Path	Non-inferiority – ReUnion RSA (A) \geq Benchmark (B, explorative meta-analysis in this document)
Hypotheses Pair	Null (H_0)
	Alternative (H_1)
Benchmark Timepoint	24 months post-operative

Benchmark n	25
Benchmark Mean	71.27 (pooled mean ASES [points])
Benchmark Std. Dev.	19.40 (pooled std. dev. ASES [points])
Benchmark Value Non-Inferiority Margin (-θ)	Pooled mean ASES minus pooled std. dev. ASES (19.40) 71.27 – 19.40 = 51.87 points
Software Used	IBM SPSS Sample Power V3.0

IBM SPSS Sample Power Output

One goal of the proposed clinical investigation is to test the null hypothesis that the population mean is 71.27 points. The criterion for significance (alpha) has been set at 0.05. The test is 2-tailed, which means that effects in both directions will be interpreted. With the proposed sample size of 10 cases, the clinical investigation will have power of 80.3% to yield a statistically significant result. This computation assumes that the population from which the sample will be drawn has a mean of 71.27 points with a standard deviation of 19.40 points. The observed value will be tested against a theoretical value (constant, non-inferiority margin) of 51.87 points.

IBM SPSS Sample Power Output – Screenshot

Estimated overall drop-out rate is 56% which leads to the requirement of enrolling additional 6 subjects into the clinical investigation.

Sample Size	Overall number of subjects to be enrolled: 16 subjects (rounded up to 20 subjects)
Overall Sample Size (multiplied by number of indications)	80 subjects

Table 2: Sample Size Justification

In conclusion, the calculated number of subjects to be enrolled (ten) plus the estimated overall drop-out rate of 56%, leads Stryker to enroll 20 subjects per cleared indication (four) to reflect the underlying subject population adequately. As a result, an enrollment target of 80 subjects in total will be aspired.

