11.3.2. Primary Analysis / Endpoint

The objective of the clinical investigation is to demonstrate the non-inferiority (equal or better) of the ASES Shoulder Score in relationship to the officially cleared indications in comparison to respective clinical outcome data in the scientific literature.

[figure not shown]
Data collection of ASES Shoulder Score will start pre-operatively and will be collected according to schedule in Table 1. This will be repeated annually in all subjects who have the prosthesis with full or partial implant survival (including all subjects without removal of all endo-prosthesis components).

The 24 months post-operative results for subjects implanted with ReUnion RSA System will be compared to a historical group and results reported by respective clinical outcome data in the scientific literature. The benchmark sources and values will serve as the control group for the ReUnion RSA System subjects.

Higher ASES Shoulder Score results are linked to better subject results and vice versa.

The clinical investigation endpoint is non-inferiority to the control, meaning the clinical investigation result should be equal or better than the control. In this clinical investigation, an equal or better ASES score result means equal or more (\geq). As only results from samples will be captured, results are mostly estimates of the true population parameter. These estimates vary by a certain area, where it is expected that the true population parameter falls within. Based on this, it is required to specify a lower limit for the acceptable difference or zone of indifference, denoted as $-\theta$.

Hypotheses are developed to allow for a comparison of the 24 months post-operative ASES score effectiveness / performance between the two underlying populations. The 24 months post-operative ASES Shoulder Score is the primary endpoint of this clinical investigation. Hypothesis tests will be one-sided with a significance level α of 5%.

Hypothesis	Equations	Interpretation
Null (H_0)	$A - B < -\theta$	Central tendency of A is inferior to the central tendency of B.
	ReUnion RSA System – Control (Benchmark) $< -\theta$	
Alternative (H_1)	$A - B \geq -\theta$	Central tendency of A is non-inferior to the central tendency of B.
	ReUnion RSA System – Control (Benchmark) $\geq -\theta$	
		
Possible Evidence (p)	Possible Decisions	Possible Conclusions – ASES score

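### The stated 80.3% power at n = 10 is for a two-tailed 5% t-test; the planned one-sided 5% t-test has 89.8%, and the same text misnames 71.27 as the null value

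*Protocol*

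**What the plan says.** **Sample-size calculation.** CIP 11.1, Table 2 sets alpha at 0.05, power at 80% and tails at 2. The software output reproduced there says "The test is 2-tailed, which means that effects in both directions will be interpreted". It names the null as follows: "One goal of the proposed clinical investigation is to test the null hypothesis that the population mean is 71.27 points". It then gives 71.27 a second role, "This computation assumes that the population from which the sample will be drawn has a mean of 71.27 points" (with an SD of 19.40), and finishes with "The observed value will be tested against a theoretical value (constant, non-inferiority margin) of 51.87 points". The resulting power at 10 cases is 80.3%. SAP 3.2, Table 3.2 carries the same text and the same figures.

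**CIP Section 11, opening text.** The protocol repeats this in its own voice. It says the study will "test the null hypothesis that the population mean is 71.27 points" and that "With the sample size of 10 cases, the clinical investigation will have power of 80.3% to yield a statistically significant result". The number of tails is not mentioned there.

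**Planned primary analysis.** CIP 11.3.2 says "Hypothesis tests will be one-sided with a significance level" of 5%. Its hypothesis table defines H0 as A − B < −θ, read as "Central tendency of A is inferior to the central tendency of B". The test is a one-sample t-test or, depending on the normality assessment, a one-sample sign test. Either is made against 51.87. SAP 3.1.1 says the same.

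**The concern.** Two core elements of the primary test, its sidedness and its null value, each have two different answers within the same document.

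On sidedness, the power was computed for a two-tailed test, but the analysis sections specify a one-sided test at the full 5%. The quoted power is then not the power of the planned test.

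On the null value, 71.27 cannot be both the value to be rejected and the value assumed to be true. The formal hypotheses put the boundary at 71.27 − 19.40 = 51.87.

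At stake is whether the sample-size justification describes the test that will be run. A reader should also be able to say, before the 24-month data are analysed, which test was planned. The choice of sidedness moves the observed mean needed to declare non-inferiority.

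**Working it through.** **Inputs** (CIP Table 2, SAP Table 3.2): assumed true mean 71.27; SD 19.40; comparison value 51.87; n = 10; alpha 0.05.

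**Effect size.** d = (71.27 − 51.87) / 19.40 = 19.40 / 19.40 = 1.00. For a one-sample t-test, df = n − 1 = 9 and the noncentrality parameter is √10 × 1.00 = 3.162.

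**Step 1: reproduce the stated figure.** Two-tailed 5% power is P(|T| > 2.2622), where T is noncentral t with 9 df and noncentrality 3.162. The result is 0.8031, which matches the stated 80.3%.

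**Step 2: the planned t-test.** One-sided 5% power is P(T > 1.8331) for the same T. The result is 0.8975, or 89.8%. The difference is 89.8 − 80.3 = 9.5 points.

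**Step 3: which test produced n = 10?**

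| n | Two-tailed 5% | One-sided 5% |
|---|---|---|
| 7 | 60.0% | 75.4% |
| 8 | 68.1% | 81.5% |
| 9 | 74.8% | 86.2% |
| 10 | 80.3% | 89.8% |

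The two-tailed test first reaches 80% at n = 10, so the stated n was derived two-tailed. The one-sided 5% test first reaches 80% at n = 8.

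**Step 4: effect on the rejection threshold.** With n = 10 and an observed SD of 19.40, the observed mean must reach:
- one-sided 5%: 51.87 + 1.8331 × 19.40/√10 = 63.12
- two-tailed 5%: 51.87 + 2.2622 × 19.40/√10 = 65.75

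**Step 5: the null as worded.** If the null and the true mean are both 71.27, then d = 0 and the rejection probability equals alpha, 5.0%. The stated 80.3% is possible only with 51.87 as the null boundary.

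**Step 6: the sign-test branch, for illustration.** At n = 10 the one-sided exact test needs at least 9 scores above 51.87 (size 0.0107; 8 or more would have size 0.0547). Its power depends on P(score > 51.87), which the documents do not give. Assumed values of 0.80, 0.841, 0.90 and 0.95 give 37.6%, 51.3%, 73.6% and 91.4%. The value 0.841 is the one implied by normality with d = 1. The 89.8% therefore cannot be carried over to this branch.

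**The case against.** **The mismatch has no practical effect.** The 9.5-point gap exists at n = 10, but the plan enrols 80 and describes one test of the 24-month scores. If the full 56% drop-out had occurred by 24 months, 80 × 0.44 ≈ 35 subjects would remain. At n = 35 and d = 1 the t-test power exceeds 99.99% on either basis. The low sign-test figures are also specific to n = 10: at n = 35 the exact one-sided test (at least 23 of 35) has 98.6% power at P = 0.80. This stands, and it is why the point is minor. It does not make the printed figure right for the printed n.

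**Two-tailed 5% is the stricter planning basis.** It is equivalent here to sizing at one-sided 2.5%, so the 80% target is met with room to spare. This also stands: the error is conservative. But keeping two tails and declaring a one-sided 2.5% test would contradict the 5% level fixed in CIP 11.3.2 and SAP 3.1.1.

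**The 71.27 null is software wording that the same paragraph corrects.** Each paragraph does go on to name 51.87, and a reader who follows the analysis sections would not test against 71.27. However, the opening text of CIP Section 11 adopts the wording as the study's own hypothesis, outside any software output.

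**With one tail, n = 8 would be enough, so the table would no longer derive n = 10.** This is fair. The revised text needs a sentence on why 10 is kept.

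**Conclusion.** The point holds and is minor. The 80.3% is the power of a two-tailed 5% t-test. The planned one-sided 5% t-test against 51.87 has 89.8% at n = 10, under the documents' own assumptions (true mean 71.27, SD 19.40, normally distributed scores). The power is understated, so there is no shortfall. The sample-size text in CIP Section 11, CIP Table 2 and SAP Table 3.2 also names the wrong null value and contradicts the formal hypotheses in the same documents. The decision rule (p ≤ 0.05, one-sided, against 51.87) and the enrolment target of 80 are unaffected.

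**What to change.** Bring the sample-size text into line with the formal hypothesis section, in both documents:

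1. In CIP Table 2 and SAP Table 3.2, set tails to 1 and remove the two-tailed sentence. Rerun the power software so that the reported output matches, and do not edit the output by hand.
2. In those tables and in the opening text of CIP Section 11, restate the t-test power at n = 10 as 89.8%. Add that 8 subjects would meet the 80% criterion one-sided and that 10 is retained.
3. In the same three places, replace the 71.27 null with wording such as: H0: central tendency below 51.87 points (A − B < −θ, θ = 19.40); assumed true mean 71.27. The term central tendency is already used in the hypothesis table and covers both the t-test and the sign test.
4. State that the power figure applies to the t-test only. Do not print a single sign-test power, because it depends on the unknown shape of a non-normal distribution.

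The cost is text edits and one software rerun. No extra subjects are needed, and alpha, the p ≤ 0.05 rule, n = 10 and the target of 80 do not change.

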9.1. INCLUSION CRITERIA

- a. Subject is willing to sign the informed consent.
- b. Subject is willing and able to comply with postoperative scheduled clinical and radiographic evaluations.
- c. Subject is male or non-pregnant female and 18 years or older at the time of surgery.
- d. Subject's joint has gross rotator cuff deficiency, a functional deltoid muscle and is anatomically and structurally suited to receive the implant and subject has one or more of the following:
 - Painful, disabling joint disease of the shoulder resulting from degenerative arthritis or rheumatoid arthritis
 - Failed previous shoulder joint replacement

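### Minor: the drop-out allowance adds 56% of 10 (16, rounded up to 20) where the stated inputs need 10/0.44, i.e. 23 enrolled; the power of the pooled primary test with 80 enrolled is not affected

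*Protocol*

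**What the plan says.** CIP Table 2 gives the drop-out input as "56% (confirmed by Medical Expert", with a literature reference. After the power output for 10 cases it states: "Estimated overall drop-out rate is 56% which leads to the requirement of enrolling additional 6 subjects into the clinical investigation". The next row reads "Overall number of subjects to be enrolled: 16 subjects (rounded up to 20 subjects", and the row after that multiplies by four cleared indications to reach 80. The conclusion of CIP 11.1 says that the ten cases plus the 56% drop-out lead to "20 subjects per cleared indication (four) to reflect the underlying subject population adequately". SAP 3.2 and its Table 3.2 repeat the same steps and figures. The SAP adds that 20 per indication is the ideal composition but not a requirement.

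The purpose of the multiplication is described in two ways at once. The introduction to CIP section 11 gives it as "multiplied by the number of cleared indications (four) to reflect the underlying subject population adequately". The opening sentence of CIP 11.1 also ties it to drop-out: "To account for an estimated appropriate overall drop-out rate, Stryker intends to enroll the calculated number of subjects, multiplied by the number of cleared indications".

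The primary analysis (CIP 11.3.2; SAP 3.1.1 and 6.6) is one one-sample test of all 24-month ASES scores against 51.87, by t-test or, depending on the normality assessment, by sign test. CIP 11.3.2 says: "Hypothesis tests will be one-sided with a significance level" of 5%. The power calculation in Table 2 is two-tailed.

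**The concern.** A drop-out rate applies to the subjects enrolled. The tables apply it to the number still needed at the end. For small rates the two approaches almost agree, but at 56% they differ clearly: 16 against 23. Rounding 16 up to 20 narrows the gap without closing it. The printed number enrolled therefore does not deliver the 10 evaluable cases on which the 80.3% rests, at the drop-out rate printed beside it.

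What is at stake is the soundness of the written justification. The conclusion of CIP 11.1 presents 20 per indication as the result of 10 cases plus a 56% allowance. A reader could take from it that each indication keeps 10 evaluable cases, and so 80% power, after the stated loss. In addition, the 56% is called an overall rate with no time point, and no loss at 24 months is stated, so the expected number of primary-endpoint scores is left open.

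**Working it through.** **Inputs** (CIP 11.1, Table 2; same in SAP Table 3.2): assumed mean 71.27, SD 19.40, comparison value 51.87, alpha 0.05, two-tailed, 10 cases, power 80.3%, drop-out 56%, four indications. From CIP 11.3.2: one pooled test, one-sided 5%.

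**Reproducing the plan's power.** Standardised effect = (71.27 − 51.87)/19.40 = 1.00. For a one-sample t-test with n cases, the noncentrality is 1.00 × √n on n − 1 degrees of freedom. At n = 10, two-tailed 5%, power is 0.8031, which is the stated 80.3%. The one-sided 5% test would give 89.8%, so the printed figure is the two-tailed t-test.

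**Reproducing the plan's enrolment.** 0.56 × 10 = 5.6, rounded to 6; 10 + 6 = 16; rounded up to 20; 4 × 20 = 80. The chain can be followed without difficulty. The step from 10 to 16 is the wrong one.

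**Correct inflation.** Enrolled N must satisfy N × (1 − 0.56) ≥ 10, so N ≥ 10/0.44 = 22.7, i.e. 23.

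**What the printed numbers leave at 56% loss.** 16 × 0.44 = 7.04; 20 × 0.44 = 8.8; 80 × 0.44 = 35.2. One-sample t-test power at effect 1.00:

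| Evaluable cases | Two-tailed 5% | One-sided 5% |
|---|---|---|
| 7 | 60.0% | 75.4% |
| 8 | 68.1% | 81.5% |
| 9 | 74.8% | 86.2% |
| 10 | 80.3% | 89.8% |
| 35 | above 99.9% | above 99.9% |

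The number of completers is itself random. Averaging power over a binomial number of completers with probability 0.44 gives, for 20 enrolled, 70.7% two-tailed and 82.4% one-sided. For 23 enrolled the same averaging gives 78.0% and 87.6%, because the standard formula secures 10 on average and not with certainty.

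**Largest loss that still leaves 10.** From 16: 1 − 10/16 = 37.5%. From 20: 1 − 10/20 = 50%. From 80: 1 − 10/80 = 87.5%.

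**Loss at 24 months.** The documents do not give it. Over an assumed range:

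| Assumed loss | Enrolled for 10 evaluable | Left of 80 |
|---|---|---|
| 10% | 12 | 72 |
| 20% | 13 | 64 |
| 30% | 15 | 56 |
| 50% | 20 | 40 |
| 56% | 23 | 35 |

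No power is quoted for the sign test. It is used only when normality fails, and the documents give no non-normal distribution from which to compute it.

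**The case against.** **Nothing in the plan depends on the step.** The test is pooled, 80 are enrolled, and at least 10 scores remain up to 87.5% loss. This stands, and it is why the point is minor. It does not make 16 the right number for the inputs beside it.

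**On the test actually planned, 20 is enough.** CIP 11.3.2 is one-sided at 5%. Eight cases already give 81.5%, and 20 enrolled average 82.4% at 56% loss. This also stands. The shortfall exists against the 10 cases and the two-tailed 80.3% that the tables themselves use; the difference in sidedness is a separate matter.

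**The 56% may not be a 24-month rate.** Outcomes run to 10 years, and the title of the cited source (CIP section 23, reference 1) refers to a minimum of 10 years. If the loss at 24 months is 50% or less, 20 suffices; at 37.5% or less, so does 16. Only the mismatch with the stated 56% is established.

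**The multiplication by four is itself the drop-out allowance.** The opening sentence of CIP 11.1 can be read that way. But both tables contain a separate drop-out step before the multiplication, and that step is the one in error.

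**A stronger reading is tempting.** A reader might infer that each indication is underpowered and that 4 × 23 = 92 should be enrolled. The documents do not support this, although the objective does mention the cleared indications. No test by indication is specified, and the SAP calls 20 per indication ideal but not necessary. The indications are also not four separate groups: CIP 9.1 requires of everyone that the "Subject's joint has gross rotator cuff deficiency, a functional deltoid muscle", which makes the first indication common to all.

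**Conclusion.** The drop-out step is wrong as written in both documents. At the stated 56% loss, 10 evaluable cases need 23 enrolled, not 16, and the rounded 20 covers losses only up to 50%. Twenty leave about 8.8 cases, with averaged t-test power of 70.7% two-tailed, but 82.4% on the planned one-sided test.

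The power of the pooled primary test is not affected: about 35 of 80 scores remain at 56% loss, with t-test power above 99.9%. That figure assumes a true mean of 71.27, an SD of 19.40, normal data and the plan's own limit of 51.87; it does not endorse that limit. It also concerns power alone. Whether the 35 remaining subjects would represent the 80 is a question of bias that this arithmetic does not answer.

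A reader might infer that the trial is too small; the documents do not support that. The point is a minor correction to the justification.

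**What to change.** Keep enrolment at 80. In CIP Table 2 and SAP Table 3.2, replace the sentence on six additional subjects and the row giving 16 rounded up to 20 with:

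> The two-tailed t-test calculation needs 10 evaluable cases; at 56% loss this requires 10/(1 − 0.56) = 23 enrolled. 80 will be enrolled; if the loss at 24 months were 56%, about 35 scores would remain, giving power above 99.9% for the pooled one-sample t-test under the stated assumptions.

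In the conclusions of CIP 11.1 and SAP 3.2, do not present 20 per indication as covering 10 evaluable cases after 56% loss. State that the 80.3% calculation does not apply to each indication after drop-out, and that the multiplication by four is for representativeness.

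State the time point to which the 56% refers and the loss assumed at 24 months.

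The cost is a few lines in each document. Enrolment, the primary test and the decision rule do not change. CIP section 15 sends amendments to the ethics board, so the CIP wording could reasonably go in with the next amendment.
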